1.0 Summary

Prospective, randomized (1:1), placebo-controlled, double blind, study of ivabradine (Corlanor®) begun at the time of discharge from the hospital or observation unit after a stay of < 48 hours from the time of admission, for a total of 28 (+/-2) days in a cohort of predominantly (but not exclusively) African American patients with acute heart failure (HF). The primary endpoint will be change in heart rate from discharge to 28 (+/-2) days. Secondary endpoint will be heart rate change in African Americans from discharge to 28 (+/-2) days. Exploratory endpoints include change in NT-proBNP, change in hs-cTnT each comparing baseline to 28 (+/-2) days. Key safety endpoints will be the rate of unplanned medical care (presentation to ED or urgent care, unplanned hospitalization, unplanned medical office visit) and days alive and out of hospital over the 28 (+/-2) days of treatment.

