5.0 Endpoints

Efficacy:

- Primary - Change in heart rate (Day 28 (+/-2) - baseline), measured by 12-lead ECG and Zio® patch (Day 14 (+/-1) - baseline).
- Secondary - Change in heart rate in self-identified African Americans (Day 28 (+/-2) – baseline), measured by 12-lead ECG and Zio® patch³(Day 14 (+/-1) - baseline).
- Exploratory:
 - 1) Change in NT-proBNP (Day 28 (+/-2) – baseline)
 - 2) Change in hs-cTnT (Day 28 (+/-2) – baseline)

Safety: Presentation for unplanned medical care in any setting within 28 (+/-2) days.

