11.0 Adverse Events or Unanticipated Problems involving Risk to Participants

All incidence of AE, AE leading to withdrawal of IP, and SAE will be reported to the IRB per institutional policies and procedures. IP will be stopped in treatment emergent clinically relevant events such as hypotension, significant dizziness, loss of consciousness, atrial fibrillation, 3rd degree AV block, and QTc prolongation. If IP is stopped, no re-challenging will be done. In case of any events between the scheduled study visits, subjects will be instructed to call the 24/7 phone number of the study team, and if clinically relevant, subjects will be asked to come in to follow up clinic for an unscheduled visit.

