13.0 Statistical Analysis

The primary outcome (change in heart rate i.e. the value at Day 28 (+/-2) - the value at baseline) will be analyzed as two sample t-test. Secondary outcomes that are continuous variables will be analyzed as two sample t-test. The safety endpoint of unplanned visits will be compared as the number of unplanned medical visits over the study period tested using Poisson regression.

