14.0 Sample Size And Power

Based on the SHIFT¹ study, the mean heart rate reduction with IVA is 8 bpm with a standard deviation of 13 bpm. A sample size of 57 in each group will have 90% power to detect a difference in means of 8.0 assuming that the common standard deviation is 13.0 using a two group t-test with a 0.05 two-sided significance level. To account for a projected dropout rate of 15%, 66 subjects will be enrolled in each group (132 total for the study over a 2-year period). Furthermore, we expect that our centers will recruit a cohort that is 75% self-identified African Americans. This number (n=99) will provide 80% power to detect the same effect size when analyzed in African Americans only.

For the safety endpoint (unplanned presentation for medical care), assuming an event rate of 25% at 1 month (estimated based on local hospital readmission rates), our sample size will provide 80% power to detect a doubling of the relative risk. If the Control group event rate is higher there will be greater power; for example, with an event rate of 35% we would have 98% power for risk ratio of 2.0 and 83% power for risk ratio of 1.75.

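### The safety visit count is tested by plain Poisson regression, whose error rate can be wrong in either direction; a patient-level robust variance and a one-sentence counting rule would correct it

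*Protocol*

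**What the plan says.** Four sections of the protocol bear on the endpoint, and they do not settle what one event is.

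- **Section 1.0** lists the kinds of care that qualify, side by side: "unplanned medical care (presentation to ED or urgent care, unplanned hospitalization, unplanned medical office visit".
- **Section 5.0** words the endpoint as "Presentation for unplanned medical care in any setting within 28 (+/-2) days".
- **Section 13.0** analyses a count, "the number of unplanned medical visits over the study period tested using Poisson regression". The SAP repeats this sentence and adds nothing on variance or counting.
- **Section 14.0** gives power for a proportion of patients, "assuming an event rate of 25% at 1 month (estimated based on local hospital readmission rates", and states that "our sample size will provide 80% power to detect a doubling of the relative risk".

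No section sets a rule for an ED presentation that ends in admission, defines an episode, or provides for overdispersion. Section 11.0 adds that after a phone call about an event, if clinically relevant, "subjects will be asked to come in to follow up clinic for an unscheduled visit". It does not say whether such a visit enters the safety count.

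**The concern.** This is the only safety comparison for which the plan names a test. A Poisson model with model-based standard errors is correct only if the variance of the count equals its mean. Two ordinary features of this setting break that.

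- **Clustering.** Some patients return more than once. ED presentation followed by admission is also a natural route for a repeat decompensation, since Section 2.0 describes patients moving from the ED to an observation unit. If both contacts are scored, events come in pairs, the variance exceeds the mean and the standard error is too small.
- **At most one event per patient.** Over 28 days many patients may have none or one. The variance is then below the mean, and the standard error is too large.

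The first case risks a false signal of harm or benefit. The second costs power to see a real one. The plan cannot tell in advance which will apply.

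**Working it through.** **The plan's own figures.** Section 14.0 gives 80% power for a 25% control rate and a risk ratio of 2.0. It adds that "with an event rate of 35% we would have 98% power for risk ratio of 2.0 and 83% power for risk ratio of 1.75". With 66 per arm and a two-sided 0.05 level (stated for the primary t-test and assumed here), a two-proportion test with continuity correction gives, for 25% against 50%:

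(0.25 − 1/66 − 1.96 × √(2 × 0.375 × 0.625/66)) / √((0.1875 + 0.25)/66) = (0.2348 − 0.1652)/0.0814 = 0.856, so power is 80.4%.

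The other two cases give 97.8% and 82.0%. The stated figures are thus reproduced to within about a point, for a yes/no outcome per patient. A Poisson Wald test with the same numbers read as mean counts gives ln 2/√(1/16.5 + 1/33) = 2.299, so power is 63.3%; the other two cases give 77.6% and 57.4%. Power was therefore planned on patients, while the test in Section 13.0 is on visits.

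**Model A: Poisson episodes.** The mean per patient is −ln(1 − 0.25) = 0.288, so that 25% of patients have at least one episode. Each episode scores 2 with probability q, otherwise 1. The mean score is 1 + q and the mean squared score is 1 + 3q, so variance/mean of the count is φ = (1 + 3q)/(1 + q).

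**Model B: at most one episode per patient.** This occurs with probability 0.25, and φ = (1 + 3q)/(1 + q) − 0.25(1 + q).

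In both models, the actual rejection rate of the nominal 5% test under no effect is 2 × (1 − Φ(1.96/√φ)).

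| q | A: φ | A: formula | A: simulated (Wald / likelihood ratio) | B: φ | B: formula | B: simulated (Wald) |
|---|---|---|---|---|---|---|
| 0 | 1.00 | 0.050 | 0.045 / 0.052 | 0.75 | 0.024 | 0.021 |
| 0.25 | 1.40 | 0.098 | 0.092 / 0.100 | 1.09 | 0.060 | 0.056 |
| 0.50 | 1.67 | 0.129 | 0.124 / 0.132 | 1.29 | 0.085 | 0.080 |
| 1 | 2.00 | 0.166 | 0.164 / 0.168 | 1.50 | 0.110 | 0.106 |

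The simulations use 57 per arm (100,000 trials per row in A, 200,000 in B). In A, 66 per arm or a 35% event rate changes little. In B, φ passes 1 when (1 + q)² = 8q, that is at q = 3 − √8 = 0.17. Below that share the test is conservative.

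**No double scoring at all.** If patients differ in their underlying rate (gamma with shape 2 down to 0.5, assumed), the plain test rejects in about 0.06 to 0.12 with q = 0. A counting rule alone would therefore not secure the error rate.

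**With a robust variance.** In model A with 57 per arm (20,000 trials each), the rejection rate is 0.047, 0.048, 0.052 and 0.045 at q = 0, 0.25, 0.5 and 1. In model B the same estimator uses the observed variance of 0/1/2 scores in place of the mean, so it removes the cause of the conservatism too.

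**The case against.** The strongest reply is that nothing here is a stated double count. Section 5.0 speaks of a presentation, and a patient admitted from the ED has presented once. The list in Section 1.0 can be read as the settings that qualify. Section 14.0 treats the outcome as one event per patient, under which nesting cannot score anyone twice. This stands: a reader might infer that the plan scores each nested contact, but the documents only leave the rule unstated. The values of q are assumptions, and q = 1 is extreme, because Section 2.0 has patients discharged directly from the ED and office visits need not lead anywhere.

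A reader might also infer that visits requested by the study team under Section 11.0 count as events, and that the team calls patients in because it sees their heart rate. The documents support neither step. Section 11.0 does not say that these visits enter the endpoint, and the reference to any setting in Section 5.0 concerns where care is given. Contact between visits starts with the patient's call. The schedule places ECGs and vital signs at the three study visits, and the patch is collected at Day 14. No section describes the team viewing heart rate in between, and no call-in rates are given from which to size a bias. Removing such visits from the main count would also be a doubtful remedy: if the drug causes symptoms that bring patients in, a safety count should show it.

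Finally, the total number of contacts is a legitimate measure of burden, and a robust variance controls the error rate even if every contact is scored. That is right, and it is why the variance is the main correction and the counting rule the lesser one.

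**Conclusion.** The concern holds as a weakness of the stated method. Plain Poisson regression on this count can reject in about 2% to 17% of null trials at a nominal 5%, depending on how visits cluster, and the plan has no provision for this. The range rests on a 25% event rate (Section 14.0), a two-sided 0.05 level carried over from the primary analysis, model-based standard errors, and q between 0 and 1, which the documents do not give. The documents do not show that the test would be anti-conservative in this trial; with single episodes and few doubles it is the reverse.

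There is no effect on reported results: the SAP states that formal analysis was not completed, with 19 of 132 enrolled. The SAP leaves later publication open, and any event summary would still need a stated counting unit.

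**What to change.** - **Section 13.0 and the SAP:** fit the Poisson model to one record per patient with a robust (sandwich) variance.
- **Section 5.0:** state that an ED presentation leading to admission counts as one event.
- **Optional:** flag visits requested by the study team on the case report form and report them by arm, without removing them from the main count.

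The cost is a sentence in each place. With overdispersed counts the interval on the log rate ratio widens by √φ: √1.40 = 1.18 times at q = 0.25, √1.67 = 1.29 at q = 0.5 and √2 = 1.41 at q = 1. That is the width the data justify. In the single-episode case with no doubling it narrows, by √0.75 = 0.87. The counting rule lowers the number of events: if half of episodes would have scored twice, the count falls from 1.5 to 1 per episode, a third fewer.

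For the 19 enrolled (13 ivabradine, 6 placebo), a sandwich variance is not dependable either. Listing events by patient and arm under the stated rule is enough.

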STATISTICAL ANALYSIS PLAN: OBSERVE-IVA

A Randomized, Double-Blind, Placebo-Controlled Trial
Assessing the Efficacy of Ivabradine Initiated at the
Time of Discharge from the Observation Unit

NCT: 03168529
8/1/2021

[name]
[contact]

Statistical Analysis Plan:

**A Randomized, Double-Blind, Placebo-Controlled Trial Assessing the Efficacy of Ivabradine Initiated at the Time of Discharge from the Observation Unit.
(OBSERVE-IVA)**

NCT: 03168529

The original plan detailed in the protocol is as follows:

13.0 Statistical Analysis The primary outcome (change in heart rate i.e. the value at Day 28 (+/-2) - the value at baseline) will be analyzed as two sample t-test. Secondary outcomes that are continuous variables will be analyzed as two sample t-test. The safety endpoint of unplanned visits will be compared as the number of unplanned medical visits over the study period tested using Poisson regression.

14.0 Sample Size And Power Based on the SHIFT1 study, the mean heart rate reduction with IVA is 8 bpm with a standard deviation of 13 bpm. A sample size of 57 in each group will have 90% power to detect a difference in means of 8.0 assuming that the common standard deviation is 13.0 using a two group t-test with a 0.05 two-sided significance level. To account for a projected dropout rate of 15%, 66 subjects will be enrolled in each group (132 total for the study over a 2-year period). Furthermore, we expect that our centers will recruit a cohort that is 75% self-identified African Americans. This number (n=99) will provide 80% power to detect the same effect size when analyzed in African Americans only.

Unfortunately, formal statistical analysis was not completed due to low sample size. Unfortunately, OBSERVE IVA fell far short of its enrollment goal with just 19 out of a targeted 132 subjects included in the final study cohort. Because of this, we have not developed any abstracts, manuscripts or other publications to date, though we may do so in the future. Of the 19 enrollments, 6 were at Detroit Receiving Hospital, 8 at Sinai-Grace Hospital, 2 at Harper University Hospital, and 3 at Henry Ford Hospital. A total of 13 subjects (68%) received ivabradine (IVA) and 6 received matching placebo.

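### Days alive and out of hospital is a key safety endpoint in the Summary but has no analysis, so death is absent from the planned safety comparison

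*Protocol*

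**What the plan says.** The Summary (protocol Section 1.0) opens its safety sentence with "Key safety endpoints will be the rate of unplanned medical care" and adds a second key endpoint, "days alive and out of hospital over the 28 (+/-2) days of treatment".

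Section 5.0 has a single safety line: "Safety: Presentation for unplanned medical care in any setting within 28 (+/-2) days". Section 13.0 has a single safety analysis, in which unplanned visits are "compared as the number of unplanned medical visits over the study period tested using Poisson regression". Section 14.0 gives power for that endpoint only: "For the safety endpoint (unplanned presentation for medical care), assuming an event rate of 25% at 1 month", the claim is that "our sample size will provide 80% power to detect a doubling of the relative risk". The SAP reproduces the Section 13.0 sentence ("The safety endpoint of unplanned visits will be compared as the number of unplanned medical visits over the study period") and adds nothing on DAOH.

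Neither document defines DAOH, assigns it a method, or says that it was withdrawn. Section 13.0 gives no exposure offset and no rule for patients who die or leave early.

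**The concern.** Of the two key safety endpoints in the Summary, only DAOH includes death, and it is the one that was not carried forward. What remains is a count of presentations for care. A patient who dies at home on Day 3 without seeking care contributes the same number of events as a patient who stays well for 28 days.

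This matters because early safety is part of the trial's stated question. Section 2.0 says that safety soon after discharge is less clear because the reference trial excluded patients within 4 weeks of discharge, and it calls this possibly a vulnerable period. A safety comparison that cannot register a death is a poor match for that question. A key endpoint with no definition and no method also leaves its calculation to be settled after the data are seen.

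**Working it through.** **1. The endpoint lists side by side**

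| Place | Unplanned care | DAOH | Death counted |
|---|---|---|---|
| Protocol 1.0 Summary | yes, as a rate | yes | through DAOH |
| Protocol 5.0 Endpoints | yes | no | no |
| Protocol 13.0 Analysis | yes, count, Poisson | no | no |
| Protocol 14.0 Power | yes, event rate | no | no |
| SAP | yes, repeats 13.0 | no | no |

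DAOH occurs once in the two documents.

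**2. The plan's own safety figures.** Section 14.0 states 80% power at a 25% control rate with a risk ratio of 2.0, and also that "with an event rate of 35% we would have 98% power for risk ratio of 2.0 and 83% power for risk ratio of 1.75". I used 66 per arm and a two-sided 0.05 level (stated for heart rate, assumed here) in a continuity-corrected comparison of proportions:

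z = [d − 1/n − 1.96·√(2p̄(1−p̄)/n)] / √{[p1(1−p1) + p2(1−p2)]/n}

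For 25% against 50%: (0.25 − 0.0152 − 0.1652)/0.0814 = 0.856, so power is 80.4%. For 35% against 70% it is 97.8%, and for 35% against 61.25% it is 82.0%. The stated 80%, 98% and 83% are reproduced to within about one point. They describe unplanned presentation and say nothing about DAOH. No DAOH power can be computed, because the documents give no mean, SD, death rate or target difference.

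**3. What deaths do to the visit count (illustration).** Assumptions: 0.25 visits per patient per 28 days while alive in both arms (borrowing the 25% event rate); two deaths at Day 3 in one arm of 66 and none in the other.

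- Expected visits with no deaths: 66 × 0.25 = 16.5.
- Visits removed: 2 × 0.25 × 25/28 = 0.45, leaving 16.05.
- Ratio without an offset: 16.05/16.5 = 0.97.
- With an offset: follow-up is 66 × 28 − 50 = 1,798 days, and 16.05/1,798 equals 0.25/28, so the ratio is 1.00.
- DAOH, setting hospital days aside: mean loss 2 × 25/66 = 0.76 day.

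**4. Range.** For an excess death proportion q at day d, the ratio without an offset is (1 − q) + q·d/28 and the DAOH loss is q(28 − d). With q = 2% at Day 14 these are 0.99 and 0.28 day. With q = 10% at Day 1 they are 0.90 and 2.7 days. With an offset the ratio is 1.00 throughout.

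**5. Precision.** With 16.5 expected visits per arm, the standard error of the log rate ratio is √(2/16.5) = 0.348, and exp(1.96 × 0.348) = 1.98. A true ratio of 1 would carry a 95% interval of roughly 0.51 to 1.98, so a shift to 0.97, or even 0.90, lies well inside it.

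**6. Window.** The exit visit may fall from Day 26 to Day 30. DAOH counted to the exit visit could differ by up to 4 days between two patients who were both well throughout. That is more than any mean loss in steps 3 and 4, so a fixed window is needed.

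**The case against.** A reader might infer that death as a competing event biases the visit comparison enough to make a harmful arm look safer. The documents do not support that. They give no mortality figure, so the deaths above are assumed. The shift appears only if exposure is ignored; the Summary calls the endpoint a rate, and Section 13.0 does not rule out an offset. Even without an offset, the shift is trivial against the interval in step 5. This part of the objection stands.

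A reader might also infer that every early death scores zero. It does not: anyone who reaches an emergency department, hospital or unplanned office visit before dying is counted for that visit.

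Nor are deaths unrecorded. Section 11.0 sends serious adverse events to the IRB, and Section 11.3 provides an independent board review. Neither is a planned between-arm comparison in the analysis section, however. The board's review was set for after 66 enrolments, and the trial stopped at 19.

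Finally, no test of DAOH would detect a few deaths. With two deaths at Day 3 in one arm and everyone else at 28 days, a rank-sum test gives p of about 0.16. The mean difference fares no better: the variance in that arm is 25² × (2/66) × (64/66) = 18.4, the standard error is √(18.4/66) = 0.53, and the 95% interval for the loss is about −0.3 to 1.8 days. This is correct, and it is a reason to estimate and display DAOH rather than rely on a test. It is not a reason to leave a named key endpoint without an analysis.

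**Conclusion.** The inconsistency is established from the text: DAOH is a key safety endpoint in the Summary and is missing from Sections 5.0, 13.0 and 14.0 and from the SAP. As a result, death is absent from the planned safety comparison. An offset would correct for shortened follow-up but would still not count the death.

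The defect lies in what the comparison measures, not in a material distortion of the visit ratio. Under the assumptions above, the ratio moves by 1% to 10% without an offset and not at all with one, while DAOH moves in the direction of harm by 0.28 to 2.7 days.

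It would also be wrong to infer that a reported result is affected. The SAP says that no formal analysis was completed, and its text reports no comparison of visits, deaths or DAOH. The practical effect is now confined to how the 13 ivabradine and 6 placebo patients are described. In a group of 6, a single death at Day 3 would move mean DAOH by 25/6 = 4.2 days, so any summary must be read as description only.

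**What to change.** For the plan:

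- List DAOH in Section 5.0 as a key safety endpoint, matching the Summary. If it was dropped deliberately, say so and remove it from the Summary.
- In Section 13.0, define it over a fixed 28-day window from discharge, with days in hospital and days after death counted as zero. State a rule for dropouts (15% are projected) and for patients whose exit visit falls before Day 28.
- Report the mean difference between arms with a 95% confidence interval.
- Tabulate deaths by arm beside the visit count.
- Add log follow-up time as an offset in the Poisson model.

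The cost is one extra analysis, some wording, and the recording of hospital admission and discharge dates. The last item cannot be assumed to exist already: Section 8.0 schedules no collection of hospital days, and adverse event reports need not hold both dates or cover planned stays.

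For the trial as it ended, with 19 patients, report deaths and DAOH by arm descriptively, without a test. If the dates cannot be recovered, report deaths by arm and say that DAOH could not be computed.

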2.0 Rationale

Ivabradine (IVA) has been shown to decrease the risk of hospitalizations for worsening HF and was associated with a trend towards improved mortality in the SHIFT¹ trial. SHIFT¹ excluded patients within 4 weeks of hospital discharge, so the efficacy and safety of IVA in this setting is less clear. In today's health care environment more and more patients that present to the ED for mild AHF are being placed into observation unit and subsequently discharged, or discharged outright from the ED. This is not only a growing segment of patients, but also represents an important window of opportunity to intervene with a potentially effective therapy.

Moreover, at this point in a patient's experience (being discharged after getting treated for exacerbation of HF), it's not clear that beta blockers (BB) should yet be increased/started due to the recent state of exacerbation. Standard treatment of worsened heart failure presenting to the ER or urgent care includes diuresis and vasodilators (e.g. ACE-I), but according to usual standard of care, titration of beta blockade is often reserved for outpatient follow up after a period of demonstrated stability (in the ambulatory setting). This is in contradistinction to hospitalized patients, where patients have been observed by the treating team for days, presumably show stability and improvement, and starting low dose BB at the time of hospital discharge has been shown to be safe (IMPACT-HF² trial). As such these ED/Observation discharge patients are often not optimal candidates for intensification of BB at the time of release, and could be considered to be at maximally tolerated BB dose (for at least for 2-4 weeks). This may represent a vulnerable period for these patients; it's unknown in the setting of Observation discharge but evidence from hospitalized patients indicates that the highest daily risk of rehospitalization is in the days just after discharge. IVA may be effective post observation unit management (where lower risk HF patients are typically placed), to reduce heart rate (without decreasing contractility, such as a BB would) to help reduce the risk of hospitalization or emergency care, but safety and efficacy (in terms of heart rate lowering) in this setting has not been previously explored.

Additionally, the SHIFT¹ trial lacked African Americans and this unique patient population has not been previously studied with IVA. The investigating sites serve a predominantly African American patient

population. Therefore the proposed study represents an important opportunity to gather data on IVA effect in this understudied group of patients.

